5.8 Treatment Visits and Assessments

IRB# 1331496 Page 27 Version 6.0

Group 1 (Healthy Volunteers): Healthy volunteers will be seen in the Critical Limb Care Center on Day 0 for Application (± 0 days) and Day 3 for Removal (± 0 days) during the study treatment period. Subjects will be instructed to call the Critical Limb Care Center [contact]) during regular business hours (0700-1600), and the Study Investigators will be available after-hours [contact] for [name], [contact] for [name], [contact] for [name])for concerns regarding adverse reactions or other general questions. Contact numbers for the study investigators will be provided in the informed consent document. The following evaluations and processes will be completed and data recorded in the REDCap eCRF:

- ♦ SAR Questionnaire (App. A)
- ♦ Concomitant medications
- ♦ Photograph (Day 3 only after the removal of the study device)

Group 2 (Wound Care Subjects): Subjects will be seen in the Critical Limb Care Center twice a week (every 3 days \pm 2 days) for up to 4 weeks. Clinical judgment of the principal or investigator will permit a subject to discontinue twice weekly bandage changes prior to the end of 4 weeks. After the first 4 weeks of treatment or when deemed permissible by the investigator, subjects will be seen in the Critical Limb Care Center weekly (7 days \pm 2 days) for a total treatment period of up to 3 months. The following evaluations will be completed and data recorded in the REDCap eCRF:

- ♦ Study device application
- ♦ Photograph of the study device application site (on Day 0 prior to study device application; following the removal of the old device and prior to application of the new device on subsequent treatment visits)
- ♦ Wound measurements
- ♦ Percent granulation tissue
- ♦ SAR Questionnaire (App. A)
- ♦ Concomitant medications

5.9 Required Follow-Up Visits and Assessments

[figure not shown]
Group 1 (Healthy Volunteers): Healthy volunteers will be seen in the Critical Limb Care Center once a week (every 7 days \pm 2 days) for a total of 4 weeks of follow-up. The following evaluations will be completed and data recorded in the REDCap eCRF:

- ♦ Photograph of the study device application site
- ♦ SAR Questionnaire (App. A)

Group 2 (Wound Care Subjects): After completion of treatment (completed when wound has healed or 3 months is reached), subjects will be seen by the principal or sub-investigator in the Critical Limb Care Center every 3 months \pm 14 days for 12 months to evaluate for any late-term issues of tolerance, side effects, and/or adverse reactions. The following evaluations will be completed and data recorded in the REDCap eCRF:

- ♦ Photograph of the study device application site
- ♦ Wound measurements
- ♦ Percent granulation tissue
- ♦ SAR Questionnaire (App. A)
- ♦ Concomitant medications

IRB# 1331496 Page 28 Version 6.0

5.10 Unscheduled Visits

A critical limb wound care podiatrist will be on call at all times.

Subjects will be instructed to call the Critical Limb Care Center [contact]) during regular business hours (0700-1600), and the Study Investigators will be available afterhours [contact] for [name], [contact] for [name], [contact] for [name]) for concerns regarding adverse reactions or other general questions. Subjects will be seen on an urgent basis as-needed based on podiatrist recommendation during regular business hours at the Critical Limb Care Center.

Unscheduled visits are additional visits that occur at times other than the protocol predetermined required visits during study participation. If an unscheduled visit occurs, the following will be collected from the subject's medical record and entered in the REDCap eCRF:

- ♦ Routine physical examination by a podiatrist, including assessment of the lower extremities
- ♦ Concomitant medications
- ♦ Photograph of the study device application site
- ♦ Wound Measurements
- ♦ Percent granulation tissue
- ♦ Bandage re-application if necessary
- ♦ SAR Questionnaire (App. A)

5.11 Subject Withdrawal or Discontinuation

Subjects have the right to withdraw from the study at any time and for any reason without penalty or loss of benefits to which the subject is otherwise entitled. If a subject decides to withdraw, all study assessments, tests, and procedures will be stopped. An exit interview will be requested to understand why the subject chose to withdraw. The subject will also be offered the option to have data collection from the electronic medical record to continue in order to track wound progression. The Investigators may withdraw the subject at any time to protect the health, safety, or welfare of the subject. At the last point of contact, the date and reason for discontinuation will be documented, and every effort should be made to follow-up the status of any ongoing adverse events prior to withdrawal.

[figure not shown]
Subjects that do not present for the initial Noxsano Bandage application appointment will be withdrawn from the study and replaced.

Study participation may continue per the Schedule of Events (section 5.1) until one of the following criteria applies:

Group 1:

♦ Unacceptable adverse reactions warranting discontinuation of treatment in the opinion of the Investigators: Subjects experiencing any allergic reaction or infection at the device application site will be removed from study treatment.

IRB# 1331496 Page 29 Version 6.0

Group 2:

- ♦ Unacceptable adverse reactions warranting discontinuation of treatment in the opinion of the Investigators: Subjects experiencing any allergic reaction or infection at the device application site will be removed from study treatment.
- ♦ *Missed weekly treatment visits and discontinuation from study treatment*: Weekly treatment visits will be indicated as "missed" if the deviation from the planned date is > 2 days (i.e., 3 or 7 days ± 2 days, during the 3 month study period). If a subject misses 2 consecutive treatment visits, they will be removed from study and not replaced.
- ♦ *Missed study follow-up visits:* Subjects who miss two consecutive follow-up visits will be contacted as described in section 5.12 in order to determine whether they wish to withdraw for the study or re-establish regular study follow-up visits. If subjects are able to re-establish study follow-up visits they may remain on the study. If the subject is unable to be contacted through the procedures outlined in section 5.12 data collection from the electronic medical record may continue, but the subject will be considered "lost to follow-up".
- ♦ Wound healing and discontinuation from study treatment: Clinical benefit may be determined during the treatment process by documentation of a healed ulceration, at which time the study device application will be discontinued. The post-treatment follow-up period will then begin for observation of late side effects and/or adverse reactions.
- ♦ *No evidence of wound healing at 2 months.* If a subject has no evidence of decreased wound surface area at 2 months (8 week treatment visit), the patient will be returned to standard and established techniques consistent with the wound etiology, and study follow-up will be discontinued.
- ♦ Wound < 50% healed at the completion of the study treatment period and discontinuation from study follow-up: If after 3 consecutive months (12 weeks) of treatment with the study device the wound does not exhibit at least a 50% decrease in surface area (cm²), the subject will be returned to standard and established techniques consistent with the wound etiology, and study follow-up will be discontinued. Clinical benefit experienced after the three-month treatment period, but not during the treatment period is not anticipated

In the absence of discontinuation due to adverse reactions (for both Groups 1 and 2) or wound healing outcomes (for Group 2 only) as indicated above, treatment may continue per the Schedule of Events (section 5.1) until one of the following criteria applies:

- ♦ Subject decision to withdraw from treatment (partial consent) or from the study (full consent),
- ♦ Death, or
- ♦ Funder reserves the right to temporarily suspend or prematurely discontinue this study.

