	Group 2 (Efficacy): Wound Care Subjects. The second phase of				
	the study is designed to determine the effectiveness of the study				
	device on wound healing in subjects with active wounds (see				
	Primary Endpoint below), and to determine if the study device				
	is equivalent to standard and established techniques (standard				
CELIDA DEGLOS	techniques demonstrate 50% wound healing at 2 months).				
STUDY DESIGN	This study is a prospective, interventional, non-randomized,				
	sequential phase study designed to assess the safety and				
	efficacy of the Noxsano Bandage (study device) in subjects				
	with a diabetic lower extremity ulceration and/or arterial				
CLIPATECE	insufficiency lower extremity ulceration.				
SUBJECT	Group 1: Initial subjects will be limited to healthy volunteers				
POPULATION	without wounds. Five (5) white subjects and 5 black or African				
	American subjects will be enrolled to evaluate skin differences.				
	Group 2: Ten (10) wound care subjects with lower extremity				
NUMBER OF	ulceration attributed to diabetes and/or arterial insufficiency.				
NUMBER OF	20 subjects will be included in the analysis (10 healthy				
SUBJECTS	volunteers for Group 1, and 10 active wound care subjects for				
NUMBER OF STEES	Group 2).				
NUMBER OF SITES	One site located at Riverside Methodist Hospital.				
PRIMARY	The primary endpoint for this study is wound healing (Group				
ENDPOINT	2), as defined by the percent change in wound surface area				
	(surface area is calculated in cm ²) from baseline through the				
CIDICALOU	active treatment period.				
SUBJECT FOLLOW-					
UP	total of 4.5 weeks. Healthy volunteers will have the study				
	device applied for 3 consecutive days (up to 72 hours),				
	followed by weekly visits for 4 weeks of observation for				
	tolerance, side effects, and adverse reactions.				
	Group 2 : The wound care subject treatment period will consist				
	of up to 3 consecutive months of study device application to a				
	specific ulceration. The study device will be changed two times				
	per week for up to 4 weeks from the start of treatment and then				

IRB# 1331496 Page 5 Version 6.0

	weekly for the remainder of the study treatment period. At the			
	conclusion of the treatment period, subjects will be followed			
	every 3 months for 12 consecutive months for observation of			
	late side effects and/or adverse reactions (up to 3 months of			
	active treatment, 12 months of follow-up observation, 15			

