5.3 Photographs

Photographs of the study device application site and wounds (Group 2) will be taken using a digital camera, an FDA Class 1 510(k) exempt medical device. Digital photographs are routinely taken in the OhioHealth Riverside Methodist Hospital Critical Limb Care Center, therefore, their equipment will be utilized for the study.

Group 1(Healthy Volunteers): A photograph will be taken on Day 0 of the shaved area on the left posterior calf prior to study device placement. A photograph of the site where the study device was applied will also be taken on Day 3, following removal of the study device, and at each follow-up visit (Days 10, 17, 24, and 31). All photographs will be

IRB# 1331496 Page 25 Version 6.0

⁶ Weeks 1-4, 2 times per week study device changes or until change to weekly is permitted by investigator.

⁷ Weeks 5-12, weekly study device changes until wound has healed or 3 months is reached.

^{83, 6, 9,} and 12 months post-treatment

uploaded into the study electronic case report forms (eCRFs) by a member of the study staff.

Group 2 (Wound Care Subjects): Photographs of the wound with a conventional ruler in place will be obtained at baseline, Day 0 (Initial Device Application), treatment, and follow-up visits. Photographs will be taken by a wound care nurse and uploaded in the study eCRFs by a member of the study staff.

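### Section 5.11 heads the missed-visit rule as stopping study treatment but words it as removal from the study, so Group 2 wound and safety data stop and their later handling is undefined

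*Combined protocol and SAP*

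**What the plan says.** The rule is one bullet under Group 2 in Section 5.11. Its heading is "Missed weekly treatment visits and discontinuation from study treatment". Its text defines a missed visit as one more than 2 days from plan, with the parenthesis "3 or 7 days ± 2 days, during the 3 month study period", and ends: "If a subject misses 2 consecutive treatment visits, they will be removed from study and not replaced". The heading speaks of weekly visits, but the parenthesis also takes in the 3-day interval of the twice-weekly phase.

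The footnotes to the Section 5.1 schedule give the visit frequency: "Weeks 1-4, 2 times per week study device changes or until change to weekly is permitted by investigator", then "Weeks 5-12, weekly study device changes until wound has healed or 3 months is reached".

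Other rules in Section 5.11 treat nearby cases differently:
- A subject with an allergic reaction or infection at the application site is removed from study treatment, not from the study.
- A subject who chooses to withdraw is offered continued collection from the medical record.
- For missed follow-up visits, "Subjects who miss two consecutive follow-up visits will be contacted as described in section 5.12". Such subjects may return, and if they cannot be reached, record collection may continue.
- The closing list separates withdrawal from treatment from withdrawal from the study.

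Section 5.9 starts the 12-month follow-up after completion of treatment, defined as healed or 3 months reached. Section 2.4 makes the secondary endpoint the proportion with at least 50% improvement in area within 2 months. Section 9 defines no analysis set and says only that imputation will be used for missing data. The Protocol Summary says "20 subjects will be included in the analysis", 10 per group.

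**The concern.** The protocol elsewhere keeps stopping the device apart from leaving the study. This bullet uses one term in its heading and the other in its text, and the difference decides whether any further data are collected.

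Read literally, study wound measurements, photographs and SAR questionnaires stop at removal. The record-collection provisions cover subjects who withdraw by choice and those lost to follow-up, but are not stated for this group. Someone removed before healing or month 3 has also not completed treatment in the Section 5.9 sense, so has no stated way into the 12-month follow-up.

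The trigger is short in weeks 1-4, and no exception is stated for absence through illness or admission. If subjects who miss visits differ in healing or harm from those who attend, the Group 2 results could be distorted. With 10 subjects, one or two removals are enough to matter. Section 9 does not say how a removed subject enters the responder proportion.

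**Working it through.** **1. The plan's own figure.** 10 healthy volunteers + 10 wound care subjects = 20, as in the Summary. The documents give no power calculation, dropout rate or miss rate, so there is nothing further to reproduce.

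**2. How quickly the rule acts** (intervals and ±2-day window from Section 5.11):
- 3-day interval: two planned visits span 2 × 3 = 6 days after the last attended visit; the second window closes at 6 + 2 = day 8.
- 7-day interval: 2 × 7 = 14 days; the second window closes at 14 + 2 = day 16.

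**3. Number of visits** (Section 5.1 footnotes, maximum schedule):
- By week 8: 4 weeks × 2 + 4 weeks × 1 = 12.
- By week 12: 4 × 2 + 8 × 1 = 16.

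**4. Chance of at least one run of two missed visits.** Assume each visit is missed independently with probability q. Let A be the probability of no run so far with the last visit attended, and B the probability of no run so far with the last visit missed. Start at A = 1, B = 0. At each visit, A becomes (A + B)(1 − q) and B becomes A·q, using the previous A and B. The removal chance is 1 − A − B.

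For example, at q = 0.10 after two visits, A = 0.90 and B = 0.09, so the removal chance is 0.01 = 0.10².

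| Assumed q | Removed by week 8 (12 visits) | Removed over 16 visits | Expected removals of 10 (16 visits) | All 10 remain (16 visits) |
|---|---|---|---|---|
| 2% | 0.4% | 0.6% | 0.06 | 94% |
| 5% | 2.6% | 3.5% | 0.35 | 70% |
| 10% | 9.7% | 13% | 1.3 | 25% |
| 15% | 20% | 26% | 2.6 | 5% |
| 20% | 32% | 41% | 4.1 | 0.5% |

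The last column is (1 − removal chance)^10. The 12-visit column is the relevant one for the secondary endpoint, because a removal in weeks 9-12 leaves the week 8 value in place. The 16-visit column is relevant to entry into follow-up.

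**5. What the undefined handling can do.** Suppose 2 of 10 are removed before any documented 50% reduction, and 4 of the other 8 respond:
- remaining subjects only: 4/8 = 50%
- removed counted as non-responders: 4/10 = 40%
- removed counted as responders: (4 + 2)/10 = 60%

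The protocol's benchmark is 50% wound healing at 2 months, so the unstated choice could decide how the result reads.

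**6. Safety information.** With no events among n subjects, the one-sided 95% upper bound on the event rate is 1 − 0.05^(1/n): 25.9% for n = 10 and 31.2% for n = 8.

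**The case against.** The case for leaving the rule alone has several sound parts.

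- **The 20 analysed.** A reader might infer that removal without replacement contradicts the Summary. The documents do not support that. Nowhere is removal said to mean exclusion from analysis, measurements taken before removal are already recorded, and imputation is planned. The number could still be 20; what is missing is a statement of how. Not replacing subjects is in itself a legitimate choice.
- **Lost week 8 data.** This applies only to removals before week 8. Earlier measurements and SAR responses remain, and ongoing adverse events are to be followed up to withdrawal.
- **Comparison with missed follow-up visits.** These are 3 months apart and involve no device, so they are not the same lapse. Different handling is not an inconsistency. The contact procedure is useful as an existing model, nothing more.
- **Direction of bias.** It is tempting to say that absentees do worse and healing will be overstated. The documents give no evidence on this, and the direction also depends on an analysis set and imputation method that are not specified.
- **The removal figures.** They rest on assumed, independent misses. An admission would cause clustered misses. Early healing or an early switch to weekly visits would reduce the number of visits.
- **Follow-up of others.** Section 5.11 also ends follow-up for subjects with no area decrease at 2 months or less than 50% decrease at 3 months, so lost late follow-up is not peculiar to this rule.

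These points narrow the claim. They do not resolve the conflict between heading and text, or the silence on data collection and analysis after removal.

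**Conclusion.** The point holds as a wording conflict with consequences for data. The heading stops treatment, the text ends study participation, and the text as written ends study wound and safety data after about 6 to 8 days of missed visits in the twice-weekly phase. That follows from the protocol alone, at any miss rate.

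How often it would happen is uncertain. Within the assumed 5-20% range the removal risk is 2.6-32% by week 8 and 3.5-41% over the full schedule; at 2% it is below 1%. Bias in the healing results and missed late harm are possible if absence is related to outcome, but neither is established. The Summary's 20 is an unresolved tension with the rule, not a contradiction. The amendment should be made because it is cheap and the group is small.

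**What to change.** 1. **Section 5.11.** Reconcile the heading and text of the missed-visit rule, and state whether it covers the twice-weekly phase. This review takes no position on device use after missed visits.
2. **Data after removal.** Whatever is decided about device use, apply the Section 5.12 contact steps. Continue the already scheduled wound measurements, photographs and SAR questionnaires at least to week 8 or, with the subject's agreement, collect from the medical record. State whether and how these subjects enter safety follow-up, in wording consistent with the Section 5.11 rules that end follow-up for non-healers.
3. **Section 9.** State that all treated Group 2 subjects are analysed. For the secondary endpoint, a documented reduction of at least 50% at any visit within 2 months makes a responder; a subject with no such observation is a non-responder. This respects the within-2-months definition in Section 2.4, so a subject who reached 50% and then missed visits is not counted as a failure. Add a sensitivity analysis on observed data.
4. **Protocol Summary.** Tie the 20 to treated subjects (10 + 10). Do not tie it to enrolled subjects: Section 4.3 counts enrolment from consent and replaces those who do not attend the first application, so more than 20 may be enrolled.

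The cost is a wording amendment, a few extra contacts on an existing visit schedule, and a responder rate that may look less favourable.

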3.3 Expected Study Duration and Subject Participation

Group 1: The initial healthy volunteer safety study will last a total of 4.5 weeks. Healthy volunteers will wear the study device for 3 consecutive days (up to 72 hours), followed by weekly visits for 4 weeks of observation for tolerance, side effects, and/or adverse reactions.

For the purposes of this study, if 2 subjects experience an unacceptable adverse reaction warranting discontinuation of treatment in the opinion of the Investigators during the initial healthy volunteer phase, the study will be halted and Group 2 (and the remainder of the initial phase, if applicable) will not be completed. Allergic reactions and infections at the study device application site will be considered unacceptable at any clinical severity; other adverse reactions will be deemed "unacceptable" by the Investigators on a case-by-case basis dependent upon clinical severity (App. A).

Group 2: The wound care subjects will have twice per week study device applications to a specific ulceration for up to the first 4 weeks of treatment and then weekly reapplication thereafter. For subjects that exhibit any reduction in wound surface area, this application will occur until the wound is healed, or for up to 3 months (whichever occurs first). For subjects that do not exhibit any reduction in wound size at 2 months, application will stop and standard treatment protocols will be pursued. At the conclusion of the treatment window (up to 3 months), subjects will be followed every 3 months for 12 consecutive months for observation of late side effects or adverse reactions (3 months of active treatment, 12 months of follow-up observation, 15 months total).

IRB# 1331496 Page 19 Version 6.0

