5.12 Lost to Follow-Up

The subject may be lost to follow-up after 3 documented phone calls and a certified letter has been mailed to the subject in order to obtain compliance with study requirements. These subjects will not be replaced.

IRB# 1331496 Page 30 Version 6.0

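### Group 2 late-safety follow-up: contact is required only after two consecutive missed 3-monthly visits, so it can start about 6 months late, and a month-12 visit missed alone requires none

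*Combined protocol and SAP*

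**What the plan says.** Section 3.3 sets the Group 2 follow-up: "subjects will be followed every 3 months for 12 consecutive months for observation of late side effects or adverse reactions". The footnote to the schedule of events places the visits at 3, 6, 9 "and 12 months post-treatment". Section 5.9 gives a window of ±14 days and the purpose: "for 12 months to evaluate for any late-term issues of tolerance, side effects, and/or adverse reactions".

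The contact rule is in Section 5.11: "Subjects who miss two consecutive follow-up visits will be contacted as described in section 5.12". The aim given there is to find out whether the subject wants to withdraw or to resume visits. If the subject cannot be reached, record review may continue and the subject is classed as lost to follow-up.

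Section 5.12 describes the procedure: "The subject may be lost to follow-up after 3 documented phone calls and a certified letter has been mailed". It sets no trigger and no time limit of its own.

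One other sentence in Section 5.11 bears on the point, "every effort should be made to follow-up the status of any ongoing adverse events prior to withdrawal", but it concerns subjects who are leaving the study. Section 5.11 defines a missed visit numerically for treatment visits only (more than 2 days off the planned date), not for follow-up visits.

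**The concern.** With visits three months apart and only four of them, a trigger of two consecutive misses uses up half the schedule before anyone is obliged to call. It also has a blind spot at the end of the schedule, because a missed month-12 visit has no later visit to pair with.

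What is at stake is late safety in a first-in-human device study. Section 7.1.1 concedes that the timing of symptoms in Group 2 cannot be stated with confidence. Under Section 7.3.1 the 2-business-day clock for reporting serious adverse events to the manufacturer starts at discovery or notification, so it cannot start for an event that nobody has heard about. When contact is finally triggered, neither Section 5.11 nor Section 5.12 says that adverse events are to be asked about.

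**Working it through.** The plan gives no figure of its own on this point, so there is nothing to reproduce. The check is calendar arithmetic and a list of patterns.

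**Inputs.** Visits at 3, 6, 9 and 12 months after treatment (schedule footnote); window ±14 days (Section 5.9); trigger of two consecutive misses (Section 5.11); 10 Group 2 subjects (Section 3.2). Assumption: 1 month = 365.25/12 = 30.44 days.

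**1. Months 3 and 6 both missed, counted from the end of treatment.**
- Miss judged on the planned date: 6 × 30.44 = 182.6 days; 182.6/365.25 = 50% of follow-up.
- Miss judged when the window closes: 182.6 + 14 = 196.6 days; 196.6/365.25 = 54% of follow-up.

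**2. General case, counted from the last attended follow-up visit.** That visit may itself fall s days from its planned date, with s from −14 to +14. Gap = 182.6 − s + a, where a = 0 (planned date) or 14 (window close).

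| Miss judged at | s = +14 | s = 0 | s = −14 |
|---|---|---|---|
| planned date | 168.6 | 182.6 | 196.6 |
| window close | 182.6 | 196.6 | 210.6 |

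The range is about 169 to 211 days (5.5 to 6.9 months), before the unspecified time for three calls and a letter.

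**3. Patterns.** Four visits, each attended or missed, give 2⁴ − 1 = 15 patterns with at least one miss.
- Contact never required (7): {3}, {6}, {9}, {12}, {3,9}, {3,12}, {6,12}.
- First required at month 6 (4): {3,6}, {3,6,9}, {3,6,12}, {3,6,9,12}.
- First required at month 9 (2): {6,9}, {6,9,12}.
- First required at month 12, when no scheduled visit remains (2): {9,12}, {3,9,12}.

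Of the seven that never require contact, {3}, {6}, {9} and {3,9} are followed by an attended visit at which history can be taken. The other three, {12}, {3,12} and {6,12}, end with a missed month 12. In those three the last 3 of 12 months (25% of follow-up) go unobserved with no contact required.

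**4. Weight of one subject.** 1/10 = 10% if all ten enter follow-up. Section 5.11 ends study follow-up for subjects with no area decrease at 2 months or under 50% decrease at 12 weeks, so the number may be smaller and 10% is a lower bound.

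**5. With a one-miss trigger at window close.** Gap for a first miss = 3 × 30.44 − s + 14, which is 91.3 days (s = +14) to 119.3 days (s = −14). All 15 patterns then require contact.

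**The case against.** The best case for the plan is that it has other ways of hearing about harm. Subjects are told to telephone with concerns, a podiatrist is always on call, and unscheduled visits collect the SAR questionnaire, a photograph and measurements (Sections 5.10 and 7.3). Monitors visit every 6 to 8 weeks and check case report forms for every subject (Section 8.2.3), so an absence should be noticed. Each attended follow-up visit is paid (Section 5.13). All adverse events after consent must be recorded (Section 7.3), so a subject who returns after an isolated miss can report what happened meanwhile. The two-visit rule was also a deliberate addition in the February 2021 amendment.

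Much of this stands, and it narrows the point. Recovery at a later visit deals with part of the loss from isolated early misses. The other safeguards either depend on the subject acting or alert staff to a blank form. None of them obliges anyone to contact the absent subject.

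A second objection is that moving the whole Section 5.12 procedure forward to one missed visit could class subjects as lost sooner, which under Section 5.13 ends further payment. That is correct, and the fix has to avoid it.

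**Conclusion.** The point holds as a cheap improvement to late-safety follow-up. The rule as written allows about 183 to 197 days after treatment before contact is required (about 169 to 211 days from the last attended visit in general), and 7 of 15 missed-visit patterns require none. The loss that cannot be recovered lies mainly in patterns that end with a missed month 12. The primary endpoint (area change during treatment) and the 2-month secondary endpoint are not touched.

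The day counts rest on a 30.44-day month and on an undefined term, since the plan does not say when a follow-up visit counts as missed.

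A reader might infer more than the documents support:
- *That such subjects are never chased.* The text only fails to require it. Section 5.12 does not forbid an earlier call.
- *That 197 days is the minimum.* It is the window-close reading; the planned-date reading gives about 183.
- *That record review is available only once a subject is lost.* Section 5.11 also offers it after withdrawal, to track wound progression.
- *That the late-safety data will be biased.* Subjects with late complications may stop attending, or may return to the limb clinic that recruited them. Selective absence is a risk, not a documented fact.
- *That Group 1 has the same defect.* Section 5.11 lists no missed-visit item for Group 1, but Section 5.12 is not limited to one group. This is an unwritten rule, not a stated rule that fails.

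**What to change.** Amend Section 5.11 so that any single missed Group 2 follow-up visit, including month 12, triggers a documented telephone contact once its +14-day window closes. At that call, record adverse events and those SAR items that can be answered by telephone. State in the same place that a follow-up visit is missed when its window closes without attendance.

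Leave the certified letter and the lost-to-follow-up classification under the existing two-consecutive-miss rule, so that one missed visit ends neither participation nor compensation.

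The cost is a short amendment and a few extra calls by existing staff, for at most 10 subjects with four visits each. The limitation is that skin signs such as erythema, edema or darkening can be reported but not examined by telephone. The study team must decide which Appendix A items suit a call, because that appendix was not in the text available for this review.
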